## **1 INTRODUCTION**

This document is a protocol for a clinical research study sponsored by Masimo Corporation. The study will be conducted in compliance with stipulations of this protocol, the conditions of IRB approval, ISO-14155, and International Conference on Harmonization Good Clinical Practice guidelines ICH E6 GCP.

### **1.1 Background and Rationale**

#### **Statement of the Problem:**

Many critically ill patients in the ICU present with significant anemia due to blood loss and body compartment fluid shifts after major surgery, trauma, coagulopathic bleeding, pathologic bleeding, or chronic disease. Maintaining euvoolemia and preventing anemia by optimization of both fluid and packed red blood cell (PRBC) transfusion management in these patients can be a daunting task. Studies in critically ill adult patients have shown that both anemia and blood transfusion can be associated with increased morbidity and mortality (1-4). Additionally, both hypo and hypervolemia may deleteriously affect organ function. (5-8). Therefore, maintaining patients within a target hemoglobin (Hb) range and rendering euvoolemia could result in improved patient outcomes.

Another challenge in the ICU is weaning ventilated patients so they can be eventually extubated or keeping patients from being intubated if they have tenuous respiratory status. The pulse oximeter and abg are currently used for these objectives. When desaturation is noted on a pulse oximeter it is often a late sign and hence limits salvage maneuvers. One of the key lab values to allow weaning of the ventilator and to know that a tenuous patient is adequately oxygenating is PaO2 from an ABG. Unfortunately getting an ABG is invasive. Also even if an arterial line is present the desire to do multiple checks is limited by resources (respiratory staff to run samples, nurse's availability to draw samples and time delay in obtaining results.)

#### **Background Information:**

Previous studies have shown that anemia in critically ill adult patients with nadir Hb less than 9 g/dl and baseline Hb less than 10 g/dl is associated with increased morbidity and mortality, even though many healthy patients can tolerate Hb as low as 5 without evidence of inadequate oxygenation (1,2). ICU patients have been shown to safely tolerate Hb levels in the range of 7-9 g/dl with decreased mortality compared to patients who are transfused to keep Hb between 10-12 g/dl. Except in patients with cardiovascular disease, such as unstable angina or myocardial infarction, there is little evidence to support transfusion of patients to Hb greater than 10 g/dl (3,9,10).

Blood transfusion carries a significant risk and critically ill patients who receive transfusions have an increased mortality versus those who do not. Additionally, there is a positive correlation between an increased ICU/hospital length of stay and the number of units of blood transfused (1,4,9). Blood transfusion also carries a risk of infection and immune mediated transfusion reactions. This creates the potential for unnecessary harm to patients if a blood transfusion is administered without a clear medical indication. Currently, blood loss is measured through monitoring drainage catheter outputs and visual inspection of blood on dressings. The patient's Hb can also be measured intermittently by various means such as arterial blood gas (ABG) analysis, or blood samples sent to the lab, which has to be done multiple times in a patient at risk and which also on its own leads occasionally to significant blood loss. The FDA has recently approved a device for use in adults that provides continuous noninvasive measurement of Hb from pulse oximetry sensors (Masimo Rainbow Co-Oximetry, Masimo Corp, Irvine, CA). This measurement is referred to as pulse hemoglobin (SpHb). The device utilizes more than 7 wavelengths of light with processed algorithms to quantify Hb species. [REDACTED]

[REDACTED]. Currently there are no studies demonstrating the utility of SpHb as a guide for transfusion management or its validity in the critically ill ICU patient. [REDACTED]

[figure not shown]
[REDACTED]

**Validation of a pulse oximetry based hemoglobin measurement system. Comparison of plethysmographic variability index to standard methods of guiding fluid and transfusion management in the critically ill adult patients. Validation of Clinical Efficacy of ORI for supplemental oxygen titration.**

**DORO0001 version 1**

It may be that continuous Hb assessment could allow more accurate titration of blood transfusion to maintain Hb levels in a target range. This may result in limiting the total number of units transfused to a patient, the amount of time a patient's Hb level is above or below the target range, and the amount of blood draws for Hb lab checks.

[REDACTED] This information can be characterized as the Oxygen Reserve Index (ORI). This index is presented on a unit-less scale between 0 and 1 that correlates with arterial oxygen concentrations between 100 and 200mmHg. This index is designed to supplement standard arterial hemoglobin saturation monitoring. (12) Preliminary studies have evaluated the relationship between ORI and paO2 in the general surgical population. (11) In addition, the ORI has been demonstrated to provide a clinically useful advanced warning of impending arterial hemoglobin desaturation in pediatric patients. (13) The relationship between ORI and standard saturation monitoring is characterized by this illustration from the above referenced whitepaper:

Oxygen Reserve Index (ORI) is an index measured noninvasively and continuously to provide an earlier indication of impending hypoxia by extending oxygen monitoring of pulse-oximetry to the moderate hyperoxic (100-200 mmHg) regions.

The device also has the capability to continuously measure the plethysmography variability index (PVI). PVI is calculated automatically and represents the variation in amplitude of the pulse oximeter waveform with respiration (22-24). PVI is analogous to stroke volume variation (SVV), which may be derived from arterial waveform, pulmonary artery catheter, esophageal Doppler, echocardiography or other device measured variations with respiration [REDACTED]

[REDACTED] Of course use of this device requires an arterial catheter be placed. Multiple studies have demonstrated that SVV is a valuable tool in predicting fluid responsiveness in mechanically ventilated patients. When SVV is elevated, patients are more likely to respond with increased stroke volume and cardiac output when fluid is administered. The threshold SVV of

---

**Validation of a pulse oximetry based hemoglobin measurement system. Comparison of plethysmographic variability index to standard methods of guiding fluid and transfusion management in the critically ill adult patients. Validation of Clinical Efficacy of ORI for supplemental oxygen titration.**

**DORO0001 version 1**

---

12% has been defined in several studies as the best cutoff value for predicting an increase in stroke volume index greater than 5% (25-32).

SVV is not the only arterial waveform derived variable that can be used to predict fluid responsiveness. Pulse Pressure Variation (PPV), which is a pressure-based dynamic variable, has been shown to correlate well with SVV in terms of predicting fluid responsiveness (9). Recently, PVI has also been shown to predict fluid responsiveness and to correlate with SVV and PPV (9). The advantage of PVI, however, is its ability to predict fluid responsiveness by non-invasive means (22-24). Improper intraoperative fluid administration has consequences for patients such as tissue hypoperfusion, increased hospital length of stay, and increased morbidity (18-21). Using PVI as an additional tool to guide fluid management may therefore have a positive impact on patient outcomes.

It is logical that Hb determination should be more accurate when the patient has near-normal intravascular volume. As stated previously, an SVV value of 12% or greater is associated with fluid responsiveness, identifying patients who have abnormally low intravascular volume. These patients may need either blood products or other fluids, as guided typically by hemoglobin measurement. When the SVV is 5% or less, the patient is considered to be normovolemic or possibly hypervolemic. The range of SVV between 6-11%, however, is less clearly defined with regards to fluid status. Recent attempts to delineate whether patients in this range would benefit from fluid administration have been successfully demonstrated in both animal and human studies. The temporary addition of PEEP to the ventilation settings and monitoring the effect on SVV can be used to show “near-hypovolemia” in mechanically ventilated patients. The addition of PEEP results in a decrease in venous return to the right heart and a subsequent decrease in left ventricular stroke volume, which may have significant physiologic effects in a borderline hypovolemic patient. When SVV increases to greater than 12% as a result of the addition of PEEP, the patient is likely hypovolemic and would benefit from a fluid bolus (Y-AA). Again, as PVI is analogous to SVV and PPV, fluid therapy has the potential to be guided by non-invasive measurements and may respond similarly to SVV when PEEP is added to patients who are nearly hypovolemic.

In addition, dynamic parameter measurements like the SVV, PVI etc, can be measured by analyzing the waveforms from various sources as listed in the Table 1 below.

| Site          | Transducer                 |  |
|---------------|----------------------------|--|
| Finger Tip    | Optical                    |  |
| Radial Artery | Pressure/Flow              |  |
|               |                            |  |
| Finger Digits | Pressure (Penaz Principle) |  |

Table 1: Hemodynamic parameter measurements waveform sources.

These measurements are affected by both volume status changes and vascular tones, although to varying degrees depending on the measurement site. Any measurement of volume status changes or vasomotor tone changes is made difficult because of the challenges in isolating the exact cause of the signal waveform attribute changes. For example the finger-tip pulse-oximeter is affected the most by vasomotor tone changes whereas the nasal alar pulse-oximeter is more effected by changes in volume status and less so by vasomotor tone. This study hypothesizes to compare the fluid status measurements obtained from various sources and measurement sites.

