## **4 SUBJECT SELECTION AND WITHDRAWAL**

### **4.1 Inclusion Criteria**

- Admitted into the SICU/8100, CTICU/7100, or NMCCS 8100 or 9100
- Aged 18 years or older
- Mechanically ventilated
- Arterial line placed
- Vigileo/Flotrac System being used for guidance of fluid management

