## 6 STUDY PROCEDURES

### 6.1 Study Procedures

Routine monitors will be used such as pulse oximeter, blood pressure cuff, 5 lead EKG and additional monitors per discretion of the treating physician. Additionally, up to eight Masimo noninvasive sensors will be placed on the fingers, hands, ears, forehead, nose (includes placement on or across alar, nasal cartilages, septum, etc.), neck, toes, feet and/or body, shielded from outside light, and attached to the Masimo Rainbow monitor. Pulse oximeter sensors will be properly aligned to ensure that the emitter and the detector are across from each other. For the sensors placed on the cavity like ala or septum, the site will be cleared of any pre-existing mucus. A standard pulse oximetry sensor will be placed on an appropriate site and attached to the standard ICU monitor. An arterial catheter will be required for enrollment into the study. A study team member will record various measurements of heart rate, arterial blood pressure, cardiac output, SVV, PPV, PVI and PI, etc. from the different devices used for comparison. High speed arterial waveform data will be electronically collected from the arterial line using data acquisition system. Ventilator waveform data may be collected from the ventilator box.

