### 6.3 Sample Collection

Each patient enrolled in this trial will have Hb measured and recorded prior to data collection. SpHb data will be obtained continuously or via spot check in SICU/8100, CTICU/7100 or NMCCS 8100 or 9100. During spot checks, blood samples must be obtained simultaneously with noninvasive reading and will thus be coordinated. SpHb will be recorded with each blood draw sample. Additional blood sampling is necessary to validate the SpHb system. For patients over 15 kg weight, at each standard of care ABG sampling an additional 4 mL of blood will be collected for patients in the SICU/8100, CTICU/7100 or NMCCS 8100 or 9100 and sent for cell count and cyanomethemoglobin determination by Masimo laboratories. These additional samples will be obtained to a maximum of 10 ABG samples per patient, only when ordered by ICU team. Thus up to 40 mL total additional blood volume may be obtained in one subject. Blood samples will be inverted or rolled 10 times to ensure proper mixing to prevent micro clotting. Patients less than 15 kg will not have any additional blood sampling done at the time of ABG analysis. All decisions regarding fluid management and the need for transfusion will be at the discretion of the attending physicians caring for the patient and will be based on the results of the clinical status and Hb measured by CBC as is customary for transfusion. The time of the CBC draw and corresponding blood samples will be noted as part of the data collection for validation of the system.

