### 6.5 Data Analysis

Statistical analyses will be performed using statistical analysis software to determine the correlation between changing hemoglobin concentrations determined by the 3 different methods and spectral absorbance. ORI data will also be analyzed to determine any correlation with PaO2 obtained by ABG. PVI data will be correlated to SVV. Outcome data will be analyzed for any relationships between the inciting event, blood loss and outcome markers to evaluate for any predictive value of inciting factors and any correlation between transfusion and fluid management variables on outcome.

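### Section 6.5 plans only a pooled correlation for hemoglobin, so any dependence of SpHb error on volume status, which Section 1.1 gives reason to expect, would be diluted or missed although SVV is recorded

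*Combined protocol and SAP*

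**What the plan says.** Section 1.1 (Background and Rationale) states that "It is logical that Hb determination should be more accurate when the patient has near-normal intravascular volume". The same paragraph ties volume status to SVV. At the upper end, "an SVV value of 12% or greater is associated with fluid responsiveness, identifying patients who have abnormally low intravascular volume", and these patients are said to need, possibly, blood products or other fluids, with hemoglobin the usual guide. At the lower end, "When the SVV is 5% or less, the patient is considered to be normovolemic or possibly hypervolemic". The range from 6% to 11% is described as less clear.

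The ingredients for relating SpHb error to SVV are planned:

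- Section 4.1 requires "Vigileo/Flotrac System being used for guidance of fluid management".
- Section 6.1 says that "A study team member will record various measurements of heart rate, arterial blood pressure, cardiac output, SVV, PPV, PVI and PI, etc", and that the arterial waveform is captured electronically.
- Section 6.3 says that "SpHb will be recorded with each blood draw sample", with up to 10 additional research samples per patient.

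For hemoglobin, Section 6.5 plans statistical analyses "to determine the correlation between changing hemoglobin concentrations determined by the 3 different methods and spectral absorbance". SVV enters Section 6.5 only as the measure with which PVI is correlated, and fluid and transfusion variables are related only to outcome. Section 2 likewise lists the SpHb and PVI comparisons separately.

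**The concern.** The protocol gives a reason to think that hemoglobin accuracy varies with volume status, and it collects a marker of volume status in the same patients. The analysis never brings the two together. Section 1.1 says that SpHb has not been validated in critically ill ICU patients, and Section 1.3 hopes for a system accurate enough to stand in for invasive measurement. A summary over all pairs answers that only on average. If SpHb did worse at high SVV, the reader would be told least about the patients for whom, by Section 1.1, hemoglobin typically guides the choice between blood and other fluids.

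The planned statistic adds to the problem. Correlation measures how well readings rank and scale together, not how far SpHb lies from the reference. Section 6.5 names no bias, error SD or limits of agreement, so the gap is wider than a missing subgroup.

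**Working it through.** The plan states no accuracy target, error SD or sample-size derivation, so there is no figure of its own to reproduce. Every numeric input below is an assumption, except the ceiling of 600 patients (Section 4.3).

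**1. Dilution of spread.** Let f be the share of pairs with SVV of 12% or more, s1 the error SD in that band and s0 the SD elsewhere, with equal bias in both.

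Pooled SD = sqrt((1 − f)·s0² + f·s1²); limits of agreement = bias ± 1.96 × SD.

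With f = 0.20 and s0 = 0.8 g/dL:

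| s1 (g/dL) | Pooled SD | Pooled limits | Limits in the band | Understatement |
|---|---|---|---|---|
| 0.8 | sqrt(0.512 + 0.128) = 0.800 | ±1.57 | ±1.57 | 0 |
| 1.0 | sqrt(0.512 + 0.200) = 0.844 | ±1.65 | ±1.96 | 0.31 |
| 1.4 | sqrt(0.512 + 0.392) = 0.951 | ±1.86 | ±2.74 | 0.88 |

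Outside the band the limits are ±1.57 throughout. Even in the last row, some of the extra error shows in the pooled figure.

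**2. What a correlation shows of a bias.** Assume a reference Hb SD of 1.5 g/dL, an error SD of 1.0 everywhere, error independent of Hb, and a bias b = +1.5 g/dL in the high-SVV band only.

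Pooled error variance = 1.0 + f(1 − f)·b²; r = 1.5 / sqrt(1.5² + error variance).

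- No bias anywhere: r = 1.5 / sqrt(3.25) = 0.83.
- f = 0.10: variance 1.2025, r = 0.81, pooled bias 0.10 × 1.5 = 0.15 g/dL.
- f = 0.40: variance 1.54, r = 0.77, pooled bias 0.40 × 1.5 = 0.60 g/dL.
- Within the band, r stays at 0.83, because adding a constant does not change a correlation.

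A 1.5 g/dL bias in the band would therefore move the planned statistic by 0.02 to 0.06.

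**3. Whether an analysis by SVV could be informative.** Assume one pair per patient, an error SD of 1.0 g/dL and a high-SVV share of 10% to 40%. The 95% half-width for the difference in bias is 1.96 × sqrt(1/n1 + 1/n0).

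| N | Half-width, share 10% (g/dL) | Half-width, share 40% (g/dL) | Power for a 0.5 g/dL difference |
|---|---|---|---|
| 600 | 0.27 | 0.16 | 96% to over 99% |
| 300 | 0.38 | 0.23 | 74% to 99% |
| 100 | 0.65 | 0.40 | 32% to 69% |

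The comparison is workable at the stated ceiling and weak if enrolment falls far short of it.

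**The case against.** The strongest reply is that the Section 1.1 sentence is a background remark, not an objective, and speaks of hemoglobin determination in general. If volume status affected every method alike, SpHb minus reference would not change with SVV. That stands as a limit: the analysis would show whether SpHb error depends on SVV, not whether the sentence is true of all hemoglobin methods. Reading it to include SpHb is still reasonable, since SpHb is what the study validates.

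A reader might infer that SpHb does fail in hypovolemic patients and that the failure would vanish in the average. The documents support neither. They give no error data, and the working shows dilution, not erasure. Nor does Section 6.5 plan pooled limits of agreement that could mislead. The 0.3 and 0.9 g/dL gaps describe what such limits would do if they were added without regard to SVV.

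A reader might also infer a risk to enrolled patients. Section 6.3 bases transfusion decisions on clinical status and CBC hemoglobin, so what is at stake is the later claim about the device.

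Three practical objections also stand. SVV recording is not tied to the blood draws. The SVV bands do not isolate normal volume, and Section 1.1 (text around Table 1) says that volume and vasomotor effects are hard to separate. Other recorded variables, such as perfusion index, could also modify the error; SVV is singled out here because the protocol itself links volume to accuracy.

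**Conclusion.** The point holds as an analysis gap that should be closed. In the available text, the only planned hemoglobin analysis is a pooled correlation, which cannot show a constant bias and would dilute volume-dependent SpHb error, while the SVV data needed to look for it are used only against PVI. The size cannot be fixed from the documents. Under the stated assumptions the understatement in the high-SVV band runs from 0 to about 0.9 g/dL, and the upper figure is one scenario, not an estimate. The conclusion rests on reading the Section 1.1 expectation as covering SpHb, and on Sections 1, 2 and 4 to 6; Section 3 and the redacted text were not available.

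**What to change.** In Section 6.5:

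1. Add SpHb-minus-reference bias and limits of agreement as the basic accuracy summary, with a patient-level random effect for the up to 10 pairs per patient.
2. Pair each blood draw with the nearest recorded SVV, or with SVV derived from the stored arterial waveform, within a stated time window. Report how many pairs have no usable SVV.
3. As a pre-specified secondary analysis, model both the mean and the spread of the error on SVV, once as a continuous variable and once by the Section 1.1 bands (5% or less, 6–11%, 12% or more). A test on the mean alone would miss the unequal-spread scenarios in the first table.
4. Report the band estimates with confidence intervals whatever the test result, so that reporting does not depend on power.

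The cost is analysis wording and time-matching work, with more effort if SVV has to be derived from waveforms. No extra sampling is needed. Some pairs will be lost for want of SVV, intervals will be wide if enrolment falls well below 600, and the results should be described as dependence on SVV, an imperfect marker of volume status.

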## **1.2 Study Devices**

The Masimo Radical-7 is a noninvasive monitor that measures arterial oxygen saturation (SpO2), pulse rate (PR), and perfusion index (PI), along with optional measurements of hemoglobin (SpHb), carboxyhemoglobin (SpCO®), total oxygen content (SpOC), methemoglobin (SpMet), Pleth Variability Index (PVI®), Oxygen Reserve Index (ORI™), Acoustic Respiration Rate (RRa®), and Pleth Respiration Rate (RRp). Masimo SET® technology is clinically proven to satisfy all sensitivity and specificity requirements for pulse oximetry. Masimo rainbow® technology uses 7+ wavelengths of light to continuously and noninvasively measure carboxyhemoglobin (SpCO), methemoglobin (SpMet), and total hemoglobin (SpHb®), as well as providing a more reliable probe-off detection. Total oxygen content (SpOC) provides a calculated measurement of the amount of oxygen in arterial blood, which may provide useful information about oxygen both dissolved in plasma and combined with hemoglobin. Perfusion Index (PI) with trending capability indicates arterial pulse signal strength and may be used as a diagnostic tool during low perfusion. Pleth Variability Index (PVI) may show changes that reflect physiologic factors such as vascular tone, circulating blood volume, and intrathoracic pressure excursions. [The utility of PVI is unknown at this time and requires further clinical studies. Technical factors that may affect PVI include probe malposition and patient motion.] Oxygen Reserve Index (ORI) is an index measured noninvasively and continuously to provide an earlier indication of impending hypoxia by extending oxygen monitoring of pulse-oximetry to the moderate hyperoxic regions. Respiration rate can be determined by the acoustic (RRa) or plethysmographic waveform (RRp). [REDACTED]

FastSat® tracks rapid changes in arterial O2. A detailed description of the Masimo Radical-7 can be found in the attached manual.

Masimo Rainbow sensors: a finger probe that consists of a series of light emitting diodes (LEDs) and photodetectors. First, light is emitted through a capillary bed; then, the sensors detect the transmitted light. The signals from the sensor are processed and used to quantify hemoglobin levels noninvasively.

Data acquisition system: consists of a hardware component connected to a laptop with data collection software used to capture wavelength data.

